3.2. Part B/C Endpoints

The primary endpoints are:

- Incidence of AEs
- Clinical assessments including but not limited to laboratory test results

The secondary endpoints are:

- PK parameters of VIR-2218 and possible metabolites (may include, but not limited to plasma: maximum concentration, time to reach maximum concentration, area under the concentration versus time curve [to the last measurable timepoint and to infinity], apparent terminal elimination half-life, clearance, and volume of distribution)
- Maximum reduction of serum HBsAg from Day 1 until Week 16
- Number of subjects with serum HBsAg loss at any timepoint
- Number of subjects with sustained serum HBsAg loss for ≥ 6 months
- Number of subjects with anti-HBs seroconversion at any timepoint
- For HBeAg-positive subjects (Part C only): number of subjects with HBeAg loss and/or anti-HBe seroconversion at any timepoint

CCI

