Alcohol intake assessment ^g		X		X	X	X	X	X	X	X	X	X	X	X	X	X
Body weight	X															
Height and BMI	X															
Vital signs ^h	X	X	X	X	X	X	X	X	X	X	X	X	X			
Safety ECG ⁱ	X	X	X				X									
Pregnancy test ^j	X	X					X				X	X	X			
FibroScan ^k	X															
Screening viral serology ^l	X															
Laboratory assessments ^m	X	X	X	X	X	X	X	X	X	X	X	X	X	X ⁿ	X ⁿ	X ⁿ
Urinalysis ^m	X	X														

Part B/C																
Study Stage	Screening	Dosing Period						Post-dose Follow-up Period ^b						Extended Follow-up Period ^c		
Study Visit Week				W1	W2	W3	W4 ^a	W5	W6	W7	W8	W12	W16	W20	W24	
Study Visit Day ± Visit Window	D -28 to -1	D1 ^a	D2	D8 ±2	D15 ±2	D22 ±2	D29 ^a ±2	D36 ±2	D43 ±2	D50 ±2	D57 ±2	D85 ±7	D113 ±7/ET	D141 ±7	D169 ±7	Q28D ±7
Urine for drugs of abuse ^o	X															
Randomization		X														
Study drug administration ^p		X					X									
Blood samples for PK analysis ^q		X	X	X			X ^r	X								
Blood sample for HBsAg	X	X	X	X	X	X	X	X	X	X	X	X	X	X	X	X
Blood sample for anti-HBs	X										X		X		X	X ^s
Blood sample for HBeAg qualitative	X															
Blood sample for HBeAg quantitative for Part C only ^t		X					X				X	X	X		X	X ^s
Blood sample for anti-HBe for Part C only	X										X		X		X	X ^s
Blood sample for HBV DNA quantitation ^u	X	X					X				X	X	X	X	X	X ^s
CCI																

Part B/C																
Study Stage	Screening	Dosing Period						Post-dose Follow-up Period ^b						Extended Follow-up Period ^c		
Study Visit Week				W1	W2	W3	W4 ^a	W5	W6	W7	W8	W12	W16	W20	W24	
Study Visit Day ± Visit Window	D -28 to -1	D1 ^a	D2	D8 ±2	D15 ±2	D22 ±2	D29 ^a ±2	D36 ±2	D43 ±2	D50 ±2	D57 ±2	D85 ±7	D113 ±7/ET	D141 ±7	D169 ±7	Q28D ±7
CCI																
Review/Record AEs ^x	X															
Concomitant Medications	X															
NUC medication adherence	X															

AE = adverse event; ECG = electrocardiogram; ET=end of treatment; **CCI** HBeAg = hepatitis e-antigen; HBsAg = hepatitis B surface antigen; HBV = Hepatitis B Virus; NUC = nucleoside/nucleotide; PK = pharmacokinetics; MAD = multiple ascending dose

Note: When scheduled at the same timepoints, the assessments of vital signs and 12-lead ECGs must be performed first, before the physical examinations, blood sample collections, and urine collections.

^a Assessments performed predose unless otherwise specified.

^b If a subject withdraws prematurely from the study prior to their Week 16 visit, ET assessments should be performed.

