^c Additional HBsAg monitoring is required for subjects with HBsAg levels with a > 10% decrease from the Day 1 predose level at the Week 16 visit. Visits will occur every 4 weeks starting at Week 20 up to Week 48 or until the HBsAg level returns to ≥ 90% of the Day 1 predose level. For example, if Day 1 predose HBsAg is 560 IU/mL and Week 16 HBsAg is 490 IU/mL, the subject will be followed until HBsAg levels returns to ≥ 504 IU/mL. Additional HBsAg monitoring may be discontinued at the Sponsor’s discretion based on emerging data.

^d A complete medical history will be taken at screening including HBV genotype if available. Any changes should be updated prior to dosing.

^e Evaluation of inclusion criteria related to urine pregnancy testing and urine drug screen.

^f See Section 7.2.1 for assessments to be performed during a full physical examination.

^g Subjects’ alcohol intake will be recorded while on study.

^h Vital signs (blood pressure, pulse rate, respiratory rate, and temperature) should be measured in the supine position after the subject has rested comfortably for approximately 10 minutes. On Day 1, vital signs should be measured within 2 hours predose and 4 hours post-dose. On all other visit days, vital signs are only required to be recorded once during the visit.

ⁱ 12-lead safety ECGs will be recorded on the timepoints listed in Appendix 5 and should be measured in the supine position after the subject has rested comfortably for 10 minutes.

^j WOCBP are required to have pregnancy tests. A serum pregnancy test will be performed at screening and urine pregnancy tests will be performed thereafter. Negative pregnancy test must be confirmed prior to study drug administration.

^k Does not need to be performed if the subject has had a FibroScan in the 6 months prior to screening or liver biopsy in the year prior to screening that confirmed the absence of Metavir F3 fibrosis or F4 cirrhosis.

^l See Section 7.1.3 for viral serology parameters.

^m Clinical laboratory and urinalysis parameters are described in Section 7.2.8.

ⁿ Liver function tests only.

^o Drugs of abuse included in the screen are described in the inclusion/exclusion criteria. Screening results for drugs of abuse must be reviewed prior to dosing.

^p Study drug will be administered via SC injection as described in Section 6.2.4.

^q Blood samples for PK analysis will be collected at the timepoints listed in Appendix 5.

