^r As a part of the Week 4 visit, subjects will return to the study center 24-hours after their initial post dose Week 4 PK sample is drawn to have a 24-hour post dose PK sample drawn.

^s Testing should occur again only at Week 36 and Week 48.

CCI

^u If a subject experiences ALT flare (as defined by ALT > 2x ULN) additional HBV DNA quantitation sample(s) may be collected

CCI

CCI

^x All AEs related to screening activities must be collected from the time of consent onwards; any other events occurring during the screening period should be reported as medical history. All SAEs must be collected from the time of consent onwards.

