3.2 Key Definitions

The following definitions will be used:

- Baseline: The baseline value is defined as the last available valid (quantifiable continuous or categorical value), non-missing observation for each subject prior to first study drug administration. Repeat and unscheduled assessments will be included in the derivation of the baseline values. Multiple pre-dose observations taken on the same date will be averaged as baseline values.
- Change from Baseline: The change from baseline value is defined as the difference between the result collected/derived at a post-baseline visit/time point and the baseline value.

The change from baseline value at each post-baseline visit/time point will be calculated for all continuous parameters using the following formula:

$$\text{Change from Baseline Value} = \text{Result at Visit/Time Point} - \text{Baseline Value}$$

The change from baseline value will only be calculated if the specific post-baseline visit/time point result and the baseline value for the parameter are both available and will be treated as missing otherwise.

- Study day: The study day of an event is defined as the relative day of the event starting with the date of the first study drug administration (reference date) as Day 1 (there will be no Day 0).

The study day of events occurring before the first study drug administration will be calculated as:

$$\text{Study Day} = (\text{Date of Event} - \text{Date of First Study Drug Administration})$$

For events occurring on or after Day 1, study day will be calculated as:

$$\text{Study Day} = (\text{Date of Event} - \text{Date of First Study Drug Administration}) + 1$$

Study days will only be calculated for events with complete dates and will be undefined for events that are 'Ongoing' at the end of the study.

Relative days compared to an alternative reference point will be calculated similarly, but the alternative starting reference start date will be used instead of the date of the first study drug dosing.

- HBsAg loss: quantitative HBsAg < 0.05 IU/mL at two or more consecutive measurements
- HBsAg Seroconversion: anti-HBs positivity at two or more consecutive measurements
- HBeAg loss (HBeAg+ subjects only): quantitative HBeAg < 0.11 IU/mL at two or more consecutive measurements
- HBeAg Seroconversion (HBeAg+ subjects only): anti-HBe positivity at two or more consecutive measurements

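### The Part C count of HBeAg loss and anti-HBe seroconversion at any time mixes unequal follow-up: sampling after Week 16 depends on the HBsAg response, and a first negative at Week 16 can be confirmed only in subjects who continue

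*SAP*

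**What the plan says.** Protocol 3.2 lists, for Part C, the "number of subjects with HBeAg loss and/or anti-HBe seroconversion at any timepoint". SAP 2.3.2 and 13.1 repeat this endpoint. The readable protocol text gives no cut-off for loss and no number of results needed. SAP 3.2 supplies both: "HBeAg loss (HBeAg+ subjects only): quantitative HBeAg < 0.11 IU/mL at two or more consecutive measurements". It defines HBeAg seroconversion in the same way, as anti-HBe positivity at two or more consecutive measurements. SAP 15 lists no change to the planned analysis.

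The Part B/C schedule (Protocol Appendix 3) places quantitative HBeAg at Day 1 and Weeks 4, 8, 12, 16 and 24. Anti-HBe is placed at screening and Weeks 8, 16 and 24. For the later visits, footnote s says of both: "Testing should occur again only at Week 36 and Week 48".

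Not every subject reaches those later visits. Under footnote c, extended monitoring is "required for subjects with HBsAg levels with a > 10% decrease from the Day 1 predose level at the Week 16 visit". It then runs as follows: "Visits will occur every 4 weeks starting at Week 20 up to Week 48 or until the HBsAg level returns to" at least 90% of the Day 1 value. The footnote adds: "Additional HBsAg monitoring may be discontinued at the Sponsor’s discretion based on emerging data".

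SAP 13.2 puts only scheduled-visit results into the antiviral summary tables, apart from the HBsAg nadir summaries.

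**The concern.** A count of events at any time compares groups fairly only if the groups are observed for similar lengths of time. Here the length of observation is set by the HBsAg result at Week 16. Protocol 1.2.2 says that NUCs do not directly affect HBsAg production and that lowering HBsAg is what sets VIR-2218 apart. Placebo subjects on NUC therapy are therefore the ones expected to leave at Week 16, and VIR-2218 subjects the ones expected to stay.

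The confirmation rule adds a second inequality. A first negative HBeAg at Week 16 needs the Week 24 sample to count. A subject who continues to Week 24 has that sample and a subject who leaves at Week 16 does not. Two subjects with identical HBeAg results through Week 16 can thus be scored differently because of their HBsAg. At stake is a named secondary endpoint in a part so small that one event among three active subjects reads as 33%.

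**Working it through.** **Inputs.** Post-baseline quantitative HBeAg at Weeks 4, 8, 12, 16, 24, 36 and 48. Post-baseline anti-HBe at Weeks 8, 16, 24, 36 and 48 (Protocol Appendix 3 with footnote s). Exit at Week 16 without a fall in HBsAg of more than 10%; otherwise exit at any four-weekly visit from Week 20 to Week 48 (footnote c). Footnote c's own example agrees with the rule: 0.90 × 560 = 504 IU/mL, and (560 − 490)/560 = 12.5%.

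**Latest scorable onset.** Under a two-consecutive rule this is the second-to-last scheduled sample at or before exit.

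| Last visit | HBeAg loss | Anti-HBe seroconversion |
|---|---|---|
| Week 16 | Week 12 | Week 8 |
| Week 20 | Week 12 | Week 8 |
| Weeks 24-32 | Week 16 | Week 16 |
| Weeks 36-44 | Week 24 | Week 24 |
| Week 48 | Week 36 | Week 36 |

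**Source of the gap.** If one negative were enough, the limits for HBeAg loss would be Week 16 (exit at Week 16) and Week 48 (exit at Week 48), a gap of 32 weeks. Under the two-result rule the gap is 36 − 12 = 24 weeks. The unequal window therefore comes mainly from the HBsAg-triggered follow-up. What the confirmation rule adds is the unequal scoring of a first result at Week 16.

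**Size under no drug effect.** The documents give no HBeAg-loss rate, so I assume a constant rate of 2-20% per year, the same in both groups. With annual probability r, h = −ln(1 − r)/52 and P(onset by week w) = 1 − exp(−h·w).

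| r | By Week 12 | By Week 36 | Ratio |
|---|---|---|---|
| 2% | 0.47% | 1.39% | 2.99 |
| 5% | 1.18% | 3.49% | 2.96 |
| 10% | 2.40% | 7.03% | 2.93 |
| 20% | 5.02% | 14.31% | 2.85 |

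These ratios apply only to subjects followed to Week 48. At r = 10%, the ratio to a Week 16 exit is about 1.0 for an exit at Week 20, 1.3 for Weeks 24-32, 2.0 for Weeks 36-44 and 2.9 for Week 48.

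**Expected events.** The planned Part C cohort has three active subjects and one placebo subject. If all three active subjects reach Week 48, the longer window adds 3 × (1.39% − 0.47%) = 0.03 to 3 × (14.31% − 5.02%) = 0.28 events. SAP 3.6 names two VIR-2218 dose groups for Part C; with three active subjects in each, the range doubles to about 0.06-0.56.

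**Losses left unconfirmed.** In a subject who leaves at Week 16, the share of onsets through Week 16 that are first seen at Week 16 is (P16 − P12)/P16. At r = 10% this is (3.19% − 2.40%)/3.19%, about 25%.

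**The case against.** A reader might infer that the protocol and SAP contradict each other, with a single negative counting under one and not the other. The documents do not support that. The protocol says when an event may occur but does not define loss; the SAP says what an event is and keeps the any-time wording. The two-result rule is an added specification, not a conflict.

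A reader might also take Week 36 as the limit for every HBsAg responder. It is only a ceiling, because subjects leave once HBsAg recovers or when the sponsor stops monitoring.

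The claim that the count favours VIR-2218 is weak at this size. SAP 3.3 plans no hypothesis tests, and the expected excess is a fraction of one event. Nor is it documented that placebo subjects all leave at Week 16. A 10% fall is only 0.046 log10 (log10 0.9 = −0.046), so some could cross the threshold by variation alone.

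The strongest defence is that the plan already has by-visit summaries. Protocol 9.7 summarises HBeAg loss and anti-HBe seroconversion by cohort and visit, SAP 13.2 gives counts at each time point, and SAP 3.1 uses subjects with non-missing data as the denominator. This helps for late visits. It does not settle Week 16: under the SAP 3.2 definition, a first negative there can be confirmed only in subjects who stay to Week 24, so even the Week 16 count is ascertained unequally.

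Some limits stand. Footnote t on the HBeAg row and the output shells are redacted, so sampling conditions or a Week 16 table may exist unseen. Visits from Week 12 on have windows of ±7 days, and an early-termination sample could serve as the second result.

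**Conclusion.** The point holds as one of unequal ascertainment. The any-time count for Part C pools subjects whose latest scorable HBeAg loss ranges from Week 12 to at most Week 36, and whose latest scorable anti-HBe seroconversion ranges from Week 8 to at most Week 36. The longer windows are open only to subjects selected by a post-baseline marker that the drug is designed to lower. The readable SAP does not say how a first negative or positive at the last available sample is scored.

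The ratio of 2.9-3.0 is an upper bound. It assumes a constant rate of 2-20% per year, placebo exit at Week 16 and active follow-up to Week 48. In expected events the effect is small and the analysis is descriptive. The change is worth making because one event can alter what this small part reports and the remedy needs no new data.

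**What to change.** In SAP 3.2 and 13.1:

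- Report HBeAg loss and anti-HBe seroconversion by group through Week 16 for all Part C subjects. Apply confirmation only with samples up to Week 16, and show first negatives or positives at Week 16 separately as unconfirmed. For anti-HBe this matters most, since only Weeks 8 and 16 are sampled after baseline in that window.
- Report events after Week 16 in a separate table with subjects in extended follow-up as the denominator.
- Keep the any-time count, with a footnote that follow-up is unequal and depends on the Week 16 HBsAg result.
- List the two-consecutive rule in SAP 15.

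The cost is SAP wording, an extra table column and one separate table; no visits, samples or subjects are added. The downside is that late events in HBsAg responders appear apart from the main between-group count.

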4.1.1. Part A Single Ascending Dose Phase in Healthy Adult Subjects

Healthy adult subjects will be enrolled in 1 of 4 planned ascending dose cohorts. At the start of each cohort, 2 sentinel subjects will be randomized 1:1 to VIR-2218 or placebo. These subjects will be dosed concurrently and monitored for 24 hours; if the investigator has no safety concerns, the remainder of the subjects in the same cohort will be dosed. Vital signs, symptom-directed physical examination(s), and AEs will be reviewed by the investigator prior to dosing any additional subjects. The remaining subjects will be randomized 5:1 to receive a single dose of VIR-2218 or placebo.

Subject screening will occur no more than 4 weeks prior to the Day 1 visit. Eligible subjects will be confined to the clinical investigative site on Day -1 to determine continued eligibility and for predose assessments. Subjects in each cohort will be randomized to receive VIR-2218 or placebo within 48 hours prior to study drug administration. Subjects will receive a single dose of study drug on Day 1 (VIR-2218 or placebo). Subjects will be discharged from the clinical investigative site after all assessments are completed on Day 2.

Subjects will return to the clinical investigative site on an outpatient basis for safety, tolerability, and PK monitoring at specified timepoints through the last Post-dose Follow-up Visit (Week 12).

Based on review of the accumulated, available data in Part A, the SRC may recommend dosing of 2 optional cohorts. In addition to the optional cohorts, up to 8 “floater” subjects for Part A may be added to any cohort, as determined and approved by the SRC (see Section 4.5.2 and Appendix 6 for further information).

Fasting is not required for any study procedure/assessment.

4.1.2. Part B/C Multiple Ascending Dose Phase in Non-Cirrhotic Adult Subjects with Chronic HBV Infection on Nucleoside/Nucleotide Therapy

Non-cirrhotic adult subjects with chronic HBV infection on NUC therapy for ≥ 6 months will be enrolled in the Part B/C cohorts. Part B will enroll HBeAg-negative subjects. Part C will enroll HBeAg-positive subjects. Eligible subjects should have HBV DNA < 90 IU/mL. Each cohort in Part B/C will be composed of 4 subjects randomized 3:1 to VIR-2218 or placebo, respectively. There are 3 planned and 2 optional cohorts in Part B. There are 1 planned and 2 optional cohorts in Part C.

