Subjects enrolled in Part B/C of the study will remain outpatient. Subject screening will occur no more than 4 weeks prior to the Day 1 visit. Eligible subjects will undergo further assessments on Day 1 to qualify for study drug administration on Day 1. To exclude the presence of cirrhosis, screening will include a mandatory noninvasive assessment of liver fibrosis such as a FibroScan evaluation, unless the subject has results from a FibroScan evaluation performed within 6 months prior to screening or a liver biopsy performed within 1 year prior to screening that confirms the absence of Metavir F3 fibrosis or F4 cirrhosis.

Subjects in each cohort will be randomized 3:1 to receive VIR-2218 or placebo within 48 hours prior to study drug administration on Day 1. Subjects will return to the clinical investigative site at Week 4 to receive a second dose of the same study drug administered on Day 1. The decision to administer a second dose will be made based on Week 3 laboratory values in accordance with dose suspension/stopping criteria in Section 4.6.

CCI

Subjects will return to the clinical investigative site on an outpatient basis for safety, tolerability, PK, and antiviral activity monitoring at specified timepoints through the last Post-dose Follow-up Visit (Week 16). Additional HBsAg monitoring is required for subjects with HBsAg levels with a $> 10\%$ decrease from the Day 1 predose level at the Week 16 visit. Visits will occur

every 4 weeks starting at Week 20 up to Week 48 or until the HBsAg level returns to $\geq 90\%$ of the Day 1 predose level. Additional HBsAg monitoring may be discontinued at the Sponsor's discretion based on emerging data.

Based on review of the accumulated, available data in Parts A, B, and C, the SRC may recommend dosing of optional cohorts following the same stratification. In addition to the optional cohorts, a combined total of up to 16 "floater" subjects for Part B/C may be added to any cohort, as determined and approved by the SRC (see Section 4.5.5 and Appendix 6 for further information).

Fasting is not required for any study procedure/assessment. The assessments performed at each visit are described in Appendix 3 .

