5.4. Part B/C Inclusion Criteria

Each subject must meet all the following inclusion criteria at screening to be eligible for enrollment in the study:

1. Age 18 (or age of legal consent, whichever is older) to 65 years at the time of screening
2. 12-lead ECG within normal limits; or, with no clinically significant abnormalities at screening, as determined by the clinical investigator
3. Female subjects must have a negative pregnancy test or confirmation of post-menopausal status. Post-menopausal status is defined as age > 50 years with no menses for at least 2 years at the time of screening. WOCBP must have a negative serum pregnancy test (using central laboratory) at screening and a negative urine pregnancy test on Day 1, cannot be breast feeding, and must be willing to use highly effective methods of contraception 14 days before study drug administration through 12 weeks after last study drug administration. Refer to Section 6.6 for more information on highly effective methods of contraception.
4. Male subjects with female partners of child-bearing potential must agree to meet 1 of the following contraception requirements from the time of study drug administration until the last follow-up visit: vasectomy with documentation of azoospermia, or male condom use plus partner use of 1 of the contraceptive options listed for contraception for WOCBP. Male subjects must also agree not to donate sperm for the 12 weeks following last study drug administration. Refer to Section 6.6 for more information on highly effective methods of contraception.

5. Agrees to not donate blood during the duration of the study
6. Willing to comply with the study requirements and able to provide written informed consent
7. BMI ≥ 18.0 kg/m² and ≤ 32 kg/m²
8. Chronic HBV infection as defined by a positive serum HBsAg for ≥ 6 months
9. On NUC therapy for at least 6 months without an interruption of 7 or more consecutive days
10. HBsAg > 150 IU/mL (by central laboratory)
11. HBV DNA < 90 IU/mL (by central laboratory)
12. Serum ALT and AST $\leq 2 \times$ ULN (by central laboratory)
13. Agrees not to increase physical activity for 4 weeks after each study drug administration

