2.3.2 Secondary endpoints

- Part A:
 - PK parameters of VIR-2218 and possible metabolites (may include, but not limited to plasma: maximum concentration, time to reach maximum concentration, area under the concentration versus time curve [to last measurable timepoint and to infinity], percent of area extrapolated, apparent terminal elimination half-life, clearance, and volume of distribution; urine: fraction eliminated in the urine and renal clearance).

- Part B/C:
 - PK parameters of VIR-2218 and possible metabolites (may include, but not limited to plasma: maximum concentration, time to reach maximum concentration, area under the concentration versus time curve [to the last measurable timepoint and to infinity], apparent terminal elimination half-life, clearance, and volume of distribution).
 - Maximum reduction of serum HBsAg from Day 1 until Week 16.
 - Number of subjects with serum HBsAg loss up to all timepoints.
 - Number of subjects with sustained serum HBsAg loss for ≥ 6 months.
 - Number of subjects with anti-HBs seroconversion at any timepoint.
 - For HBeAg-positive subjects (Part C only): number of subjects with HBeAg loss and/or anti-HBe seroconversion at any timepoint.

CCI

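### HBeAg loss is scored on a quantitative cut-off with no Day 1 condition, so a Part C subject already below it before dosing could be counted as a responder

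*SAP*

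**What the plan says.** The Part C secondary endpoint in SAP 2.3.2 is the "number of subjects with HBeAg loss and/or anti-HBe seroconversion at any timepoint". SAP 13.1 repeats it among the antiviral activity variables.

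SAP 3.2 defines loss as "quantitative HBeAg < 0.11 IU/mL at two or more consecutive measurements". The line opens with a population limit, "HBeAg loss (HBeAg+ subjects only"), but gives no quantitative meaning for that status. The companion definition of HBeAg seroconversion asks for anti-HBe positivity at two or more consecutive measurements and sets no starting condition.

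On entry, Protocol 4.1.2 says "Part C will enroll HBeAg-positive subjects" and gives no threshold. Sections 5.4 and 5.5 contain no HBeAg criterion. The Part B/C schedule (Protocol Appendix 3) has two HBeAg rows:

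- "Blood sample for HBeAg qualitative": Screening only, Day -28 to -1.
- "Blood sample for HBeAg quantitative for Part C only": Day 1 and Week 4 (both predose under footnote a), Weeks 8, 12, 16 and 24, then Weeks 36 and 48. There is no Screening sample.

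Anti-HBe (Part C) is drawn at Screening, Weeks 8, 16 and 24, then Weeks 36 and 48. There is no Day 1 sample.

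**The concern.** Loss means going from present to absent. The rule tests only the second half. The first half is left to Part C membership, which seems to come from a different measurement, taken up to four weeks earlier, whose cut-off is not stated. If a subject is positive on the qualitative test but below 0.11 IU/mL on Day 1, the rule can be met by a flat profile. Because Day 1 is not excluded as one of the two consecutive measurements, Day 1 and Week 4 alone could be enough.

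The composite has the same weakness on its other side: a subject who is anti-HBe positive at Screening and stays positive meets the seroconversion wording.

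What is at stake is a small descriptive count. With three active subjects per cohort, one misclassified subject changes what the table appears to show.

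**Working it through.** **Inputs.** Cut-off and two-measurement rule: SAP 3.2. Sampling times: Protocol Appendix 3. Cohorts of 4 randomized 3:1, with 1 planned and 2 optional Part C cohorts: Protocol 4.1.2. Part C dose groups (50 mg and 200 mg): SAP 3.6.

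**The plan's own figure.** Part C cohorts: 3 × 4 = 12 subjects, which agrees with Protocol 5.1. At 3:1 this is 9 active and 3 placebo, before floaters.

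**Step 1: does eligibility close the gap?** For HBsAg it does. Entry requires "HBsAg > 150 IU/mL (by central laboratory") and SAP 3.2 sets the HBsAg loss cut-off at 0.05 IU/mL: 150 / 0.05 = 3,000, so every subject starts far above the cut-off. HBeAg has no such floor. The Day 1 quantitative HBeAg sample is not an entry condition either: "Subjects in each cohort will be randomized 3:1 to receive VIR-2218 or placebo within 48 hours prior to study drug administration on Day 1", and the only HBeAg result scheduled before that visit is the qualitative one.

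**Step 2: apply the rule to illustrative profiles** (IU/mL at Day 1, Weeks 4, 8, 12 and 16; invented values, used only to test the logic).

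| Profile | As written, Day 1 may count | As written, post-dose values only | With Day 1 ≥ 0.11 and post-dose values |
|---|---|---|---|
| 0.10 throughout | loss | loss | not loss |
| 0.10, 0.10, 0.2, 0.2, 0.2 | loss | not loss | not loss |
| 5, 1, 0.2, 0.1, 0.1 | loss | loss | loss |
| 5 throughout | not loss | not loss | not loss |

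Limiting the rule to post-dose values removes the second profile but not the first. The Day 1 condition is needed as well, and the true decline is kept.

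**Step 3: do other SAP rules catch it?** SAP 14 replaces a result below the quantitation limit with the limit minus one significant digit, so a result reported as < 0.11 would become 0.10 and meet the cut-off. The SAP 3.2 baseline must be a valid, quantifiable value. A Day 1 result below quantitation may not qualify, and there is no other predose quantitative HBeAg sample, so change from baseline could be missing for exactly these subjects.

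**Step 4: effect of one such subject on the proportion.**

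| Part C as | Active | Placebo |
|---|---|---|
| One cohort of 4 | 1/3 = 33 points | 1/1 = 100 points |
| Two dose groups of 4 (assumed size) | 1/6 = 17 points | 1/2 = 50 points |
| Three cohorts, no floaters | 1/9 = 11 points | 1/3 = 33 points |

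The placebo figures mainly reflect how few placebo subjects there are.

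**The case against.** The strongest reply is that the mechanism is not demonstrated. The documents give neither the qualitative assay's cut-off nor its agreement with 0.11 IU/mL. If the two agree, a discordant subject must have fallen below the cut-off in the 28 days or less before Day 1. This stands: the text shows that a no-change responder is possible, not that one is likely.

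Second, the population limit in the definition could be read as already requiring positivity at baseline. No section defines HBeAg+ quantitatively, and no section ties it expressly to the qualitative test. That link is an inference from the schedule. It is a reasonable one, because the qualitative test is the only HBeAg test scheduled at Screening.

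Third, the footnote to the quantitative HBeAg row is redacted and could bear on this measurement. That lowers confidence.

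Fourth, the consequence is limited. SAP 3.3 plans no hypothesis tests, SAP 11 plans no efficacy analysis, and safety is the primary objective. SAP 13.2 lists all antiviral data and shows categorical results at baseline and at each later time point, and Protocol 9.7 summarizes HBeAg by visit. A careful reader of the listings would find such a subject. This also stands, but the endpoint count itself would still include that subject.

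**Conclusion.** The gap in the written rule is real. It lacks both a Day 1 condition and a post-dose limit, and nothing visible elsewhere supplies them. One affected active subject is worth 33, 17 or 11 percentage points, depending on how many Part C cohorts are run. The 17-point figure assumes that the two dose groups in SAP 3.6 have 4 subjects each. The conclusion also assumes that Part C status comes from the qualitative Screening test and that the redacted footnote does not add the missing condition.

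Two stronger readings are not supported. A reader might infer that the endpoint cannot be read as an effect of VIR-2218. That goes too far for a descriptive count accompanied by subject-level listings and a placebo group. A reader might also attach a probability by assuming a discordance rate. The documents offer no anchor for one, and the chance of a single low Day 1 value is not the chance of a false responder, because the rule needs two consecutive low values.

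This is a correction worth making to a secondary definition. It does not affect the trial's primary objective.

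**What to change.** In SAP 3.2, define HBeAg loss as a Day 1 predose quantitative HBeAg result of at least 0.11 IU/mL, followed by values below 0.11 IU/mL at two or more consecutive measurements after the first dose. Base the Day 1 condition on the reported result itself, not on the derived baseline, because of the quantifiable-value wording. Use the number of evaluable subjects as the denominator, and list those below 0.11 IU/mL on Day 1.

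For the and/or endpoint, also require anti-HBe to be negative at Screening, the only predose anti-HBe sample, and positive at two or more consecutive post-dose measurements. Without this, a no-change subject could still enter the composite through the antibody component.

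The cost is SAP wording and a few derivation conditions on samples already scheduled. The downside is that the Part C denominator may fall by one or two subjects, which is noticeable in groups this small; showing the evaluable number makes that visible.
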